- (E3) how the number of consultations delivered in primary care develops in the first two years after introducing POCUS use in general practice including the variation over time and between GPs.
- (E4) how the GPs' reported effect of POCUS on their clinical decision and patient management in general practice develops in the first year after introducing POCUS use in general practice.
- (E5) the number of unwanted cases associated with the use of POCUS reported by the participating GPs in the first two years after introducing POCUS use in general practice.

Outcomes to assess implementation strategy effects:

- (I1) Adoption: the proportion of participating GPs that adopt the intervention and start using POCUS in their daily practice during the educational interventions (months 1-3).
- (I2) Fidelity (adherence): the proportion of participating GPs that complete the educational elements in the intervention (pre-post tests, webinars, assignments, attendance on seminar days, logbook registrations).
- (I3) Reach (penetration): The proportion of teachers who actively support participants by engaging in the online part of the educational interventions
- (I4) Sustainability (maintenance): the proportion of participating GPs that adopt the intervention and continue to use POCUS in their daily practice following the educational interventions (months 5-6).

Outcomes to inform further development of the implementation strategy

- (D1) Adaptability: the extent to which the teachers and participants find that the implementation of the educational intervention meets local needs
- (D2) Acceptability: the extent to which the teachers and participants find the implementation of the educational interventions is agreeable in terms of content and delivery
- (D3) Feasibility: the extent to which the teachers and participants find the educational intervention to be suitable for implementation
- (D4) Compatibility (appropriateness): the extent to which the teachers and participants perceive the implementation of the educational intervention is in line with the organisation's values, mission, priorities
- (D5) Dose (satisfaction): the extent to which the teachers and participants are satisfied with the amount of support and resources received as part of implementation strategy
- (D6) Complexity: the extent to which the teachers and participants perceive the implementation of the educational intervention as being difficult or complex

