- (D6) Was the educational intervention too difficult or complex to implement?
- (D7) Did any organisational political, economic or social factors influence the implementation of the educational intervention?
- (D8) Did the setting, including organisational values or norms influence the implementation of the educational intervention?
- (D9) Did you have the capacity (e.g. knowledge and skills) to implement the educational intervention?

And the following questions with a free-text answer category:

- (D10) How must did you have to invest financially to implement the educational intervention?
- (D11) How much time and resources did you have to invest to implement the educational intervention?

Outcomes to assess the feasibility of trial methods

For the assessment of the feasibility of trial methods (outcomes F1-F8), we will evaluate the data quality by calculating the proportion of missing or incomplete registrations, recruited participants in relation to possible number of participants as well as participant retention and adherence. The steering committee will discuss the results and perform a qualitative evaluation based on predefined progression criteria (see section 16c).

Regarding the GP questionnaire (outcome F8), we will pilot test validated scales to determine GPs' perceived stress (Cohen's 10-item Perceived Stress Scale), GPs' job satisfaction (Warr-Cook-Wall Job satisfaction Scale) and GPs burnout symptoms (Maslach Burnout inventory).

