After the educational intervention, we will perform a process evaluation by collecting and assessing a number of implementation-related outcomes. We will use predefined progression criteria for all outcomes to make an interim analyses and evaluate whether adaptions to the intervention is needed prior to the large stepped wedged cluster randomized clinical trial (SW-CRT). The steering committee will perform this evaluation.

We will consider changing the intervention and/or implementation strategy if:

Implementation strategy effects:

- (I1) Adoption: less than 80% percent of participating GPs adopt the intervention and start using POCUS in their daily practice during the educational interventions (months 1-3).
- (I2) Fidelity (adherence): less than 75% of participating GPs complete the educational elements in the intervention (pre-post tests, webinars, assignments, attendance on seminar days, logbook registrations).
- (I3) Reach (penetration): less than 90% of teachers will actively support participants by engaging in the online part of the educational interventions
- (I4) Sustainability (maintenance): less than 75% of participating GPs adopt the intervention and continue to use POCUS in their daily practice following the educational interventions (months 5-6).

Development of the implementation strategy

- (D1) Adaptability: Less than 90% of teachers or participants find that the implementation of the educational intervention meets local needs
- (D2) Acceptability: Less than 90% of teachers or participants find the implementation of the educational interventions is agreeable in terms of content and delivery
- (D3) Feasibility: Less than 90% of teachers or participants find the educational intervention to be suitable for implementation
- (D4) Compatibility (appropriateness): Less than 90% of teachers or participants perceive the implementation of the educational intervention to be in line with the organisation's values, mission, priorities
- (D5) Dose (satisfaction): Less than 90% of teachers or participants are satisfied with the amount of support and resources received as part of implementation strategy

- (D6) Complexity: More than 90% of teachers or participants perceive the implementation of the educational intervention as being difficult or complex
- (D7) Context: More than 90% of teachers or participants find that organisational political, economic or social factors influenced the implementation of the educational intervention

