- (D8) Culture: More than 90% of teachers or participants find that the setting, organisational values or norms influenced the implementation of the educational intervention
- (D9) Self-efficacy: Less than 90% of teachers or participants find that they had the capacity (e.g. knowledge and skills) to implement the educational intervention
- (D10) Cost: if costs of implementation the educational intervention exceeds the budget for the research project
- (D11) Resources: if measures of the resources and managing required for the implementation the educational intervention exceeds the budget for the research project

Feasibility of trial methods

- (F1) if we are not able to recruit 66% of the eligible participants
- (F2) if we are not able to retain 66% of participants
- (F3) if we are not able to retain 90% of teachers
- (F4) if less than 90% of teachers delivered the intervention by protocol
- (F5) if less than 90% of participants received the intervention by protocol
- (F6) if less than 90% of data from registers was obtainable and valid
- (F7) if less than 90% of data collection through GP questionnaires was obtainable and valid
- (F8) if less than 90% of data collection through GP questionnaires was obtainable and valid

17 Blinding

[figure not shown]
The researcher cleaning the data set and responsible for analyzing the primary outcome will have no knowledge of participants. He is a researcher with a physiotherapy background.

Data collection, management, and analysis

18a Data collection - Plans for assessment and collection of outcome, baseline, and other trial data

Data will be collected at different timepoints.

Figure 7. Data collection

Register data: Data regarding different POCUS examinations, number of referrals, number of consultations will be delivered by PLSP (outcomes E1-3, I1 and 4). The data are registered prospectively by GPs in the medical records during the consultations from the first teaching seminar (day 7) until 24 months after the first teaching seminar (day 829). We will receive these data retrospectively from PLSP, who will use an algorithm to collect monthly aggregated data for each participating GP.

PLSP will also deliver aggregated data on patients age and gender independent from other study data.

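### Progression criterion D6 (complexity) is met only when more than 90% of a group report the problem, so among 21 GPs it stays unmet at 18 adverse answers

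*Protocol*

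**What the plan says.** Section 16c describes an evaluation by the steering committee after the educational intervention: "We will use predefined progression criteria for all outcomes to make an interim analyses". The list opens with "We will consider changing the intervention and/or implementation strategy if".

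- **Favourably worded items.** D1 reads "D1) Adaptability: Less than 90% of teachers or participants find that the implementation of the educational intervention meets local needs". D2-D5 follow the same pattern, as does D9: "D9) Self-efficacy: Less than 90% of teachers or participants find that they had the capacity (e.g. knowledge and skills) to implement the educational intervention".
- **Adversely worded item.** D6 reads "D6) Complexity: More than 90% of teachers or participants perceive the implementation of the educational intervention as being difficult or complex".
- **Items without direction.** D7 and D8 have the same form as D6, for example "D8) Culture: More than 90% of teachers or participants find that the setting, organisational values or norms influenced the implementation of the educational intervention".

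The wording of D6 is not constant. Section 7 defines the outcome as "the extent to which the teachers and participants perceive the implementation of the educational intervention as being difficult or complex", which matches the criterion. The question in section 12 is "D6) Was the educational intervention too difficult or complex to implement", answered on a 5-point Likert scale.

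Section 20a says D1-D9 will be reported as an average score. The analysis plan is to be uploaded before the analysis at 24 months.

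**The concern.** A favourable statement that must reach 90% tolerates up to 10% of answers that are not favourable. The matching rule for an adverse statement would be met once more than 10% agree. D6 instead tolerates up to 90% agreement, nine times the share, and section 16c gives no reason for treating complexity so differently.

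The purpose of 16c is to identify what may need changing before the large trial, and D6 is its only criterion on complexity. As written, a large majority of GPs can report the problem without the criterion being met.

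The change of wording matters too. A yes to too difficult is plainly adverse. A yes to difficult need not be, for a demanding course. The criterion and the question therefore do not measure quite the same thing.

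D7 and D8 ask whether factors had an influence, without saying whether it was good or bad. More than 90% agreement there has no clear adverse meaning.

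**Working it through.** **Inputs.** The thresholds are those of section 16c, read with the strict inequalities as printed. The number of GPs is uncertain in the protocol itself, so four values are used:
- 20, the target in the registration table;
- 21, the expected number in section 14;
- 24, because section 14's 66% of 36 is 0.66 × 36 = 23.76, which does not reproduce its 21 (21/36 = 58%);
- 36, all course places.

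All GPs are assumed to respond, and teachers and participants are judged as separate groups.

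**Counts.** D6 is met at the smallest k with k/n > 0.9. D1 is met at the smallest number m of not-favourable answers with (n − m)/n < 0.9.

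| n | D6 unmet up to | D6 first met | D1 first met (not favourable) |
|---|---|---|---|
| 20 | 18 (90%) | 19 (95%) | 3 (15%) |
| 21 | 18 (86%) | 19 (90.5%) | 3 (14%) |
| 24 | 21 (88%) | 22 (92%) | 3 (12.5%) |
| 36 | 32 (89%) | 33 (92%) | 4 (11%) |

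The number of teachers is not given. With 10 or fewer, k/n > 0.9 requires every teacher to report difficulty.

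**Chance that D6 is met.** With X binomial(n, p), where p is the assumed true adverse share:
- p = 0.8: P(X ≥ 19 | 20) = 0.07; P(X ≥ 19 | 21) = 0.18; P(X ≥ 22 | 24) = 0.11; P(X ≥ 33 | 36) = 0.05.
- n = 21: 0.0001 at p = 0.5 and 0.027 at p = 0.7.

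**Same p = 0.8, D1 tolerance.** P(X ≥ 3) for n = 20, 21 and 24, and P(X ≥ 4) for n = 36, all exceed 0.999.

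**Does the result hang on 10%?** No. With n = 21, a rule of more than 50% (11 or more) is met with probability 0.974 at p = 0.7 and 0.999 at p = 0.8.

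**Price of the D1 tolerance.** The chance that it is met when few are unfavourable:

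| True unfavourable share | n = 20 | n = 21 | n = 24 | n = 36 |
|---|---|---|---|---|
| 10% | 0.32 | 0.35 | 0.44 | 0.49 |
| 5% | 0.08 | 0.08 | 0.12 | 0.10 |

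**Mean versus percentage (secondary).** Assume that scores of 4-5 count as favourable, n = 21:
- 17 fives and 4 twos: mean (85 + 8)/21 = 4.43, favourable 17/21 = 81%, so a D1-type criterion is met.
- 19 fours and 2 threes: mean (76 + 6)/21 = 3.90, favourable 19/21 = 90.5%, so it is not met.

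The higher mean goes with the met criterion, so an average score cannot decide a percentage rule.

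**The case against.** **The evaluation takes place anyway.** The committee sees the D6 answers whether or not the threshold is crossed, and crossing it only means that a change is considered. This stands, and it limits the harm. But marking when to consider change is the whole job of a progression criterion, and one that is unmet at 86% adverse answers does not do it.

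**Other routes exist.** D3, D9, the teachers' answers, the final plenary, and the adoption, completion and delivery criteria (I1, I2, F5) could all expose a course that is too hard. With 21 GPs, D3 or D9 would each be met with probability 0.82 if 20% were not favourable, and 0.97 if 30% were not. This also stands: the probabilities given for D6 are for D6 alone, not the chance that the whole evaluation misses the problem.

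**The scales are not identical.** Not favourable on D1 can include neutral answers, while D6 counts agreement with an adverse statement. With no Likert cut-off stated, the factor of nine compares the printed thresholds, not a measured ratio. The counts for D6 itself are unaffected.

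**A demanding course may fairly be called difficult.** That could support a tolerance wider than 10% for the criterion's wording. It does not support 90%, and it does not fit the question asked, which is about being too difficult.

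**The 10% tolerance prompts often.** With 21 GPs, a rule of more than 25% (6 or more) would be met with probability 0.014 at a true 10% and 0.987 at 50%. That is a reasonable alternative if the sponsor states and justifies it.

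**It may be too late.** The seminars ended in November 2022 and the questionnaire was due at day 97, so the decision may already have been taken. This affects how the correction is made and reported; the criterion is wrong as written either way.

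**Conclusion.** The concern holds. D6 carries the 90% of the favourable items with only the inequality reversed. Taken alone, it stays unmet in the participant group at 18/20, 18/21, 21/24 or 32/36 adverse answers. At an assumed true adverse share of 80% it would be met with probability 0.05 to 0.18. The conclusion does not depend on which group size is right or on the choice of 10% as comparator. It rests on full response, on binomial sampling for the probabilities, and on judging each group separately; under that reading the teachers could still meet D6 on their own.

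The consequence is moderate: an advisory criterion fails on the one topic it covers, with other criteria as partial cover. The effectiveness outcomes E1-E5 are untouched. The points on D7-D8 and on the average score are secondary. The percentages can be tabulated from the same answers, although section 20a does not name them and the analysis plan may come later than the 16c evaluation. The correction should be made, as it is cheap.

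**What to change.** 1. **D6 threshold.** Restate D6 in 16c on the tolerance of D1-D5 and D9: change is considered if fewer than 90% of participants, or fewer than 90% of teachers, answer that the intervention was not too difficult or complex. Neutral answers then count as they do for D1. If a wider tolerance is intended for a demanding course, print the figure and the reason.
2. **D6 wording.** Use the questionnaire's phrase, too difficult or complex, in the criterion.
3. **D7-D8.** Either state what an adverse answer is, or make these items descriptive and amend the claim in 16c that criteria exist for all outcomes.
4. **Section 20a (clarification).** For D1-D9, report the proportion at a stated Likert cut-off, by group, alongside the mean.

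The cost is wording in 16c and 20a; no new data are needed. The price is that the criterion will be met more often: with 21 GPs, probability about 0.35 when the true unfavourable share is exactly 10%, a rate that each of D1-D5 and D9 already carries. If the answers have already been seen, report D6 under both the printed and the revised rule and label the revision as made later.

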Continuous medical education for GPs is centrally organized under the wings of the Organisation of General Practitioners in Denmark (Praktiserende Lægers Organisation PLO) that has an educational branch (PLO-e). PLO-e is the practical organizer of the ultrasound course delivered in this educational intervention. PLO-e had no influence on the scientific content or data collection in the study.

The study will be coordinated from CAM AAU and data will be collected by the research team at the training sessions and by the participating general practitioners in their clinics. All study data will be stored at a secure server at Aalborg University.

Some of the GPs participating in this study may later on be eligible to have the course fee reimbursed and receive payment for the scans (approximately DKR 262 per scan). A decision regarding this lies not with the research team, but will depend on matters relating to the general practice agreement between PLO and the Danish Regions. A decision regarding this is expected in September 2022.

10 Participants

All GPs participating in two ultrasound courses organized by PLO-e (course number 9018822 and 9017222) are eligible to participate in this study. Independent of previous use of ultrasound in general practice, participants had to meet the following criteria:

Inclusion criteria:

1. Postgraduate medical doctor with a specialization in general practice
2. Working in office-based Danish general practice
3. Access to an ultrasound device in the practice during the study period

Exclusion criteria:

1. Not willing to participate in the data collection or share data for this study
2. No signed informed consent to participate

[figure not shown]
All patients seen in general practice, that the GPs find relevant to examine with POCUS can be used in the data collection. For this study, we will not collect identifiable personal or health-related data on patients. However, we will receive aggregated data on patients' age and gender. These data are used to describe the patient population but will neither be stored with the other study data nor used in analysis with other data (see section 12).

11a Description of the intervention

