For the registration of unwanted cases (outcome E5), we will use a questionnaire giving the GPs the possibility to explain in free text using their own words to explain (1) what was scanned, (2) circumstances surrounding the scan, (3) what happened, and (4) reflections after the scan. Data will be collected from baseline to 24 months after baseline. We will report the aggregated total number of monthly registrations for each participating GP. The free text elaborations will not be reported, but passed on to the safety committee (see section 5d). The assessment of unwanted cases for the study does not substitute the GP's registration of untoward incidents required by Danish law (<https://stps.dk/da/ansvar-og-retningslinjer/vejledning/rapporteringspligt/>).

Outcomes to assess implementation strategy effects:

For the assessment of implementation strategy effects (outcomes I1-4), we will use the register data (fee specific codes) collected by PLSP on the monthly use of POCUS for each participating GP (outcomes I1 and I4) and the activities logged (pre-post tests, webinars, assignments, attendance on seminar days, logbook registrations) in the online platform used in the educational intervention (outcomes I2-3) to estimate the frequency of use and the percentage of adherence, respectively. The continues data (outcomes I1 and I4) will be collected prospectively from day 7 to day 372, while the binary data (outcomes I2 and I3) are collected retrospectively at the end of the educational intervention including registration made in the online platform from day 1 to day 97 (at the end of the educational intervention).

Outcomes to inform further development of the implementation strategy

For outcomes related to the development of the implementation strategy (outcomes D1-D11), we will use a questionnaire distributed to participants three months after introducing POCUS in

general practice and teachers following the final teaching seminar (day 97). A reminder will follow after 2 weeks. The questionnaire will include the following questions with a 5-point Likert scale:

- (D1) Did the educational intervention meets local needs?
- (D2) Was the educational interventions agreeable in terms of content and delivery?
- (D3) Was the educational intervention suitable for implementation?
- (D4) Was the educational intervention in line with your values, mission, priorities?
- (D5) Are you satisfied with the amount of support and resources allocated to you?

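### D7 and D8 record whether context or culture influenced implementation but not in which direction, while section 16c uses the count as if influence were adverse

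*Protocol*

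**What the plan says.** Protocol section 12 introduces the D1 to D9 items with: "The questionnaire will include the following questions with a 5-point Likert scale". The D7 item is "Did any organisational political, economic or social factors influence the implementation of the educational intervention", and the D8 item is "Did the setting, including organisational values or norms influence the implementation of the educational intervention". Free-text answers are planned only for D10 and D11. Section 20a reports D1 to D9 as an average score.

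Section 16c opens its list with "We will consider changing the intervention and/or implementation strategy if". The D7 entry is "More than 90% of teachers or participants find that organisational political, economic or social factors influenced the implementation of the educational intervention", and the D8 entry is "More than 90% of teachers or participants find that the setting, organisational values or norms influenced the implementation of the educational intervention". The outcome definitions in section 7 are equally neutral about direction.

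Section 9 says that there is no fee for POCUS in primary care and that GPs pay for the device and the training themselves. It then says: "Some of the GPs participating in this study may later on be eligible to have the course fee reimbursed", together with a payment of about DKR 262 per scan. Section 15 limits free attendance and the scan fee to the GPs furthest from a radiology department.

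**The concern.** A progression criterion needs a favourable and an unfavourable side. The other Likert-based criteria in section 16c have one: D1 to D5 and D9 are met when too few respondents give the favourable answer, and D6 when too many find the intervention difficult or complex. D7 and D8 take over the 'more than 90%' form of D6, but their items have no unfavourable side. The rule therefore reads influence as a problem when the item has not established that it was one.

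What is at stake is the use of these two outcomes. They are meant to inform the implementation strategy before the stepped-wedge trial. A high count could mean that context blocked the GPs, that it carried them, or some of each. These call for different responses, and the recorded result would not tell them apart.

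**Working it through.** The Protocol states no design figure on this point, so there is nothing to reproduce. The check compares wording and then counts.

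**Wording.** D7 and D8 appear in three places: the outcome definitions (section 7), the questionnaire items (section 12) and the criteria (section 16c). In all three the verb is 'influence', with nothing on direction. No companion item or free-text field for D7 or D8 supplies it, and an average score cannot recover it.

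**Count needed.** The criterion is met at the smallest k with k/n > 0.90. Inputs for n, participants only (the number of teachers is not given):
- 20: target sample size in the registration table at the front of the Protocol.
- 21: expected GPs, section 14.
- 24: section 14 gives 66% of 36 as 21, but 0.66 × 36 = 23.76, so 24 is shown as well.
- 36: all course places, section 15.

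| n | smallest k | k/n | one fewer |
|---|---|---|---|
| 20 | 19 | 95.0% | 18/20 = 90.0%, not above 90% |
| 21 | 19 | 90.5% | 18/21 = 85.7% |
| 24 | 22 | 91.7% | 21/24 = 87.5% |
| 36 | 33 | 91.7% | 32/36 = 88.9% |

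**Direction, n = 21.** Let h be the number helped and b the number hindered, each respondent counted once. The criterion as written uses (h + b)/21. A criterion on hindrance with the same cut-off uses b/21.

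| h | b | as written | hindrance only |
|---|---|---|---|
| 19 | 0 | 19/21 = 90.5%, met | 0/21 = 0%, not met |
| 10 | 9 | 19/21 = 90.5%, met | 9/21 = 42.9%, not met |
| 0 | 19 | 19/21 = 90.5%, met | 19/21 = 90.5%, met |

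Three opposite or mixed situations give the same result under the rule as written. The splits are illustrations, not forecasts.

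**Whether both directions are plausible here.** Section 9 names a possible hindrance (no fee, own equipment and training costs) and a possible help (reimbursement and scan payment for some), with the payment decision expected in September 2022. The third seminars are dated 29 and 30 November 2022 (section 13), and the questionnaire follows them (section 18a). A paid and an unpaid GP could both truthfully answer that economic factors had an influence and mean opposite things.

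**The case against.** The strongest reply is that an undirected prompt is defensible. If nearly everyone says that context shaped implementation, even favourably, the team should ask whether the strategy would work where that context is absent. Payment for only some GPs is a case in point. This stands as a reason to keep asking about helpful influence. It does not justify adding helpful and hindering answers together, because one raises a question of transferability and the other a question of repair.

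A reader might also infer more than the Protocol supports:

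- **That any influence, or a favourable context, would force a change.** Section 16c only commits the team to consider one, and only above 90%. Section 12 gives the judgement to the steering committee as a qualitative evaluation, and the committee can ask about direction before acting.
- **That the new payment would by itself meet D7.** Sections 9 and 15 restrict it to some GPs and do not give their share. Nothing shows that 19 of 21 would credit it.
- **That the answer sheets of helped and hindered GPs would be identical.** The anchors of the 5-point scale are not given. Directed anchors cannot be excluded, although the question wording does not suggest them. Even with such anchors, the section 16c criterion as worded would count both directions.
- **That the study learns nothing about barriers.** The motivational descriptions (section 11a) ask about barriers, the third seminar includes an evaluation questionnaire and a plenary session, and D10 and D11 ask in free text about money, time and resources. None of these replaces a directed D7 or D8 answer, but they give the committee something to go on.

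**Conclusion.** The point holds as a minor flaw in measurement and in the criterion. As worded, D7 and D8 cannot separate barriers from support, and section 16c treats the undirected count as a warning sign. With 21 GPs, 19 reports of influence meet the criterion whatever their direction.

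It affects two of the eleven development outcomes and no effectiveness outcome. Its practical effect is limited by the wording of section 16c, the qualitative committee review and the other information on barriers. The count assumes 21 respondents and looks at participants alone. The statement that direction goes unrecorded assumes Likert anchors that follow the neutral question wording. Whether 90% is the right level is a separate matter.

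**What to change.** Replace D7 and D8 in section 12 with two 5-point items each, one asking how far the named factors helped implementation and one how far they hindered it. One respondent can then report both. In section 16c, base the D7 and D8 criteria on the 'hindered' items and state which scale points count. Report the 'helped' items descriptively, as a transferability question for the stepped-wedge trial. Align the definitions in section 7.

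The seminar dates in section 13, and the reference in section 25 to register data becoming available only in November 2024, suggest that the questionnaires may already be back. If so, report D7 and D8 descriptively, state openly that direction was not recorded and that meeting the criterion cannot be read as adverse, and use the directed items in the next trial. Make this a disclosed change, since silently dropping a predefined criterion after the answers are in would be worse than the flaw.

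The cost is two extra Likert items per respondent and a few changed lines in sections 7, 12 and 16c.
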